9.2.3. Pruritus

For patients who report AEs consistent with pruritus at the visit, a qualified staff member will administer the Pruritus Numerical Rating Scale (see Appendix 8 of the study protocol). The Pruritus Numerical Rating Scale assesses a patient’s severity of itching on average and at its worst point, in the past 24 hours, on a scale of 0 (no itching) to 10 (worst imaginable itch).

Treatment-emergent pruritus is defined as any preferred term including “Prur”. Pruritus will be summarized overall with

An overall summary of pruritus will be presented by treatment group. The number and percentage of patients who experience at least one of the following:

- Any Pruritus TEAE, All CTCAE grades
- Pruritus TEAEs by Maximum Severity (Grade 1, 2, or 3)
- Serious Pruritus TEAE
- Treatment-related Pruritus TEAE, All CTCAE grades
- Treatment-related Grade 3 or higher Pruritus TEAE
- Treatment-related serious Pruritus TEAE
- Pruritus TEAE leading to study drug interruption
- Pruritus TEAE leading to study drug discontinued
- Pruritus TEAE leading to discontinuation from the study

A separate by-patient listing for pruritus events will be provided with associated Pruritus Numerical Rating Scale results, if applicable.

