Study Day	Screening -56 to Day -1	Day 1	15	29	43	57	85	113		Visit windows post randomization through Week 12: ± 3 days from the specified study day. Visit window Week 16: -1 week /+2 days from the specified study day.
Transient Elastography	X									A historical transient elastography report within 3 months of Screening may be used to determine eligibility for this study. See inclusion/exclusion criteria for details.
MRI-PDFF ^d	X				X		X		X	A Screening MRI-PDFF may proceed on the basis of the initial ALT/AST level at Screening, given all other eligibility criteria are met, but randomization should not occur prior to confirmation of ALT/AST stability as necessary. An MRI-PDFF should be performed at ET only if not done within the prior 4 weeks, and the patient has had at least 4 weeks of dosing.
Drug Accountability			X	X	X	X	X		X	

Visit	Screening	Treatment Period ^c						Follow-Up ^b	ET ^a	Notes
		Week 0	Week 2	Week 4	Week 6	Week 8	Week 12			
Study Day	Screening -56 to Day -1	Day 1	15	29	43	57	85	113		Visit windows post randomization through Week 12: ± 3 days from the specified study day. Visit window Week 16: -1 week /+2 days from the specified study day.
Adverse Events Review	X	←	←=====→				→	X	X	After informed consent but prior to initiation of study drug, all AEs and SAEs related to protocol-mandated procedures should be reported. All AEs and SAEs, regardless of cause or relationship, will be collected from the start of study drug through the Follow-Up Period.
Pruritus Assessment		←	←=====→				→	X	X	Reported AEs consistent with pruritus will be assessed using a numeric scaling tool (Appendix 8).
Concomitant Medications Review		←	←=====→				→	X	X	

a Patients discontinuing the study at any time for any reason (Early Termination) should complete the ET visit as soon as feasible and return for a Follow-Up 4 weeks (-1 week /+2 days) after the last dose of study drug.

b The Follow-Up may take place at Week 16 (-1 week /+2 days) or 4 weeks (-1 week /+2 days) after the last dose of study drug if patients discontinue the study at any time for any reason (Early Termination).

c Samples collected during the treatment period should be collected pre-dose

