8.5.6. Assessment of Pruritus

For patients who report AEs consistent with pruritus, photographs of the affected area(s) will be taken at the discretion of the Investigator (eg, if there are visible skin lesions; photos that would identify the patient, ie, of the entire face, will be avoided), and a qualified staff member will administer the Pruritus Numerical Rating Scale ([Appendix 8](#)) at each study visit where pruritus is reported or noted to be ongoing. If pruritus is reported, the clinical site will provide details on these events in the eCRF.

The Investigator will be asked to provide an assessment of the severity of the AE using the NCI CTCAE v5.0 categories for pruritus as follows:

- Grade 1: Mild or localized; topical intervention indicated.

- Grade 2: Widespread and intermittent; skin changes from scratching (eg, edema, papulation, excoriations, lichenification, oozing/crusts); oral intervention indicated; limiting instrumental activities of daily living (ADL).
- Grade 3: Widespread and constant; limiting self-care, ADL, or sleep; systemic corticosteroid or immunosuppressive therapy indicated.

For Grade 3 cases, follow up by telephone contact or in person visit should occur within 3 days or at the discretion of the Investigator. Additional follow up may take place until symptoms improve. Refer to [Section 7](#) for additional information on study drug discontinuation.

[REDACTED]

[REDACTED]

[REDACTED]

[REDACTED]

[REDACTED]

9. Statistical Considerations

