If an event does not meet the AE definition, then it cannot be an SAE even if serious conditions are met (eg, hospitalization for signs/symptoms of the disease under study, death due to progression of disease).

Recording and Follow-Up of an AE and/or SAE

AE and SAE Recording

• When an AE and/or SAE occurs, it is the responsibility of the investigator to review all documentation (eg, hospital progress notes, laboratory reports, and diagnostics reports) related to the event.• The investigator will then record all relevant AE and/or SAE information in the eCRF.• It is not acceptable for the investigator to send photocopies of the patient’s medical records to the Sponsor or designee in lieu of completion of the AE or SAE eCRF.• There may be instances when copies of medical records for certain cases are requested by the Sponsor or designee. In this case, all patient identifiers, with the exception of the patient number, will be redacted on the copies of the medical records before submission to the Sponsor or designee.

• The investigator will attempt to establish a diagnosis of the event based on signs, symptoms, and/or other clinical information. Whenever possible, the diagnosis (not the individual signs/symptoms) will be documented as the AE and/or SAE.
Assessment of Intensity

The Investigator will be asked to provide an assessment of the severity of the AE using NCI CTCAE v5.0 categories as follows:
 
• Grade 1: Mild; asymptomatic or mild symptoms; clinical or diagnostic observations only; intervention not indicated.• Grade 2: Moderate; minimal, local, or noninvasive intervention indicated; limiting age appropriate instrumental ADL.• Grade 3: Severe or medically significant but not immediately life-threatening; hospitalization or prolongation of hospitalization indicated; disabling; limiting self-care ADL.• Grade 4: Life-threatening consequences; urgent intervention indicated.• Grade 5: Death related to AE.
Assessment of Causality

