2.2.4. Treatment Assignment, Blinding, and Randomization Methodology

Patients will be randomized to TERN-101 or placebo using an Interactive Web Response System (IWRS). Approximately 96 patients will be randomized at an overall ratio of 1:1:1:1 into 4 groups receiving 5 mg (n = 24), 10 mg (n = 24), 15 mg (n = 24) TERN-101 tablet, or matching placebo (n = 24). Randomization will ensure 6 patients at each TERN-101 dose level and 6 patients in the placebo group are assigned to the PK/PD sub-study.

Investigators, patients, all study personnel, and the Sponsor will remain blinded to each patient's assigned dose group throughout the course of the study. The randomization codes will be provided to bioanalytics to allow for the exclusion of placebo patients from the PK assay.

Bioanalytics will not disclose the randomization code or the results of their measurements until the trial is officially unblinded.

Emergency unblinding procedures are outlined in Section 6.4.1 of the study protocol and in the unblinding plan.

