9.2.2. Patient Incidence of Adverse Events

Summaries will be displayed by SOC and PT, and will be ordered by descending order of all TERN-101 incidence of system organ class and preferred term within each system organ class. Summaries of the following types will be presented:

- Patient incidence of TEAEs by MedDRA SOC and PT. [REDACTED]
- Patient incidence of TEAEs by MedDRA SOC, PT, and highest severity (CTCAE grade). At each level of patient summarization, a patient is classified according to the highest severity if the patient reported 1 or more events. AEs with missing severity (CTCAE grade) will be considered Grade 3 (severe) for this summary.
- Patient incidence of CTCAE Grade 3 or higher TEAEs by MedDRA SOC and PT. At each level of patient summarization, a patient is classified according to the highest severity if the patient reported 1 or more events. AEs with missing severity (CTCAE grade) will be considered Grade 3 (severe) for this summary.
- Patient incidence of treatment-related TEAEs by MedDRA SOC and PT. Related AEs are those with relationships reported as “Definitely Related” or “Possibly Related”. At each level of patient summarization, a patient is classified according to the closest relationship to study drug if the patient reported 1 or more events. AEs with a missing relationship will be considered related for this summary.
- Patient incidence of treatment-related CTCAE Grade 3 or higher TEAEs by MedDRA SOC and PT. At each level of patient summarization, a patient is classified according to the highest severity if the patient reported 1 or more events. AEs with missing severity (CTCAE grade) will be considered Grade 3 (severe) for this summary. AEs with a missing relationship will be considered related for this summary.
- Patient incidence of serious TEAEs by MedDRA SOC and PT.
- Patient incidence of TEAEs leading to study drug discontinued by MedDRA SOC and PT. This is a subset of the AEs where Action Taken with Study Drug is checked as “Study drug discontinued.”

The following listings will be presented by treatment group and patient, include study day event started and the duration of event:

- All adverse events.
- Serious adverse events (subset of the AEs where serious is marked as “Yes”).
- CTCAE Grade 3 or higher adverse events (subset of AEs where severity is marked as CTCAE Grade 3, 4, or 5).
- Related adverse events (subset of the AEs where relationship marked as “Definitely Related” or “Possibly Related”).

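### Pruritus is scored on clinical judgement but counted on a text string, so a site-identified itch event coded to another term is missing from the pruritus summary

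*SAP*

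**What the plan says.** **Collection.** The protocol's Schedule of Activities states: "Reported AEs consistent with pruritus will be assessed using a numeric scaling tool". Protocol 8.5.6 uses the same trigger: "For patients who report AEs consistent with pruritus, photographs of the affected area(s) will be taken at the discretion of the Investigator". The rating scale is then given at each visit where itch is reported or continuing, and the investigator grades the event on the CTCAE categories for pruritus. The section adds: "If pruritus is reported, the clinical site will provide details on these events in the eCRF".

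**Recording.** Protocol Appendix 6, under AE and SAE recording, says: "Whenever possible, the diagnosis (not the individual signs/symptoms) will be documented as the AE and/or SAE".

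**Counting.** SAP 9.2.3 repeats the clinical trigger for the scale ("For patients who report AEs consistent with pruritus at the visit, a qualified staff member will administer the Pruritus Numerical Rating Scale") and then gives its only visible case definition: "Treatment-emergent pruritus is defined as any preferred term including" the string 'Prur'. The overall pruritus table follows, with rows for any event, maximum grade, seriousness, relatedness, interruption and discontinuation. A separate by-patient listing of pruritus events carries the rating-scale results.

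**Elsewhere.** SAP 9.2.2 plans "Patient incidence of TEAEs by MedDRA SOC and PT", together with a listing of all adverse events. SAP 4.1 and 4.3 place eCRF data in by-patient listings. SAP 11, which lists changes from the protocol's analyses, does not mention pruritus.

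**The concern.** Within SAP 9.2.3, the patients who are scored and the patients who are counted are selected by different rules. Scoring depends on the site's judgement that an event looks like pruritus. Counting depends on how the recorded term was coded. The visible text does not compare the two sets.

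The protocol's own rules open a route between them. Protocol 8.5.6 expects some itch cases to have visible skin lesions (its example for taking photographs), and its Grade 2 wording describes skin changes from scratching. Under the Appendix 6 preference for a diagnosis, such a case could be entered as a skin condition.

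Safety is the primary objective. Pruritus has its own protocol section, rating scale, Grade 3 follow-up and summary table. Protocol 2.2.3 reports no pruritus in the 119 subjects dosed so far, so this table would be read as the first such evidence in patients. A reader would reasonably expect it to cover the cases that the sites identified.

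**Working it through.** **1. A figure to reproduce.** There is none. The visible text gives no expected pruritus rate, and safety is descriptive. The check is therefore a comparison of rules followed by an illustration of size.

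**2. One event traced through the rules.** Suppose a site sees an itching patient with skin lesions and records a skin diagnosis whose preferred term lacks 'Prur'.
- Rating scale given (Protocol 8.5.6, SAP 9.2.3): yes.
- Pruritus details entered in the eCRF (Protocol 8.5.6): yes, since itch was reported.
- Counted in the pruritus table (SAP 9.2.3): no.
- In the pruritus listing with scores (SAP 9.2.3): no, if the listing uses the section's definition.
- In the general TEAE tables and the all-AE listing (SAP 9.2.2): yes, under its own term.
- Score and eCRF details listed somewhere (SAP 4.1, 4.3): yes.

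**3. Weight of one patient.** SAP 2.2.4: "Approximately 96 patients will be randomized at an overall ratio of 1:1:1:1 into 4 groups", so 96/4 = 24 per arm and 3 × 24 = 72 on TERN-101.
- One arm: 1/24 = 4.2 points.
- Pooled TERN-101: 1/72 = 1.4 points.

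Examples with exact (Clopper-Pearson) 95% intervals, one patient coded elsewhere:
- 2/24 = 8.3% (1.0 to 27.0) becomes 1/24 = 4.2% (0.1 to 21.1).
- 5/24 = 20.8% (7.1 to 42.2) becomes 4/24 = 16.7% (4.7 to 37.4).

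**4. Sensitivity to unknown inputs.** Let p be the true share of an arm with itch, and f the share of those patients whose only itch event is coded without 'Prur'. Neither is in the documents; both ranges are assumptions. Reported rate = p(1 − f). Expected patients missed per arm = 24pf. Chance of missing at least one in an arm = 1 − (1 − pf)^24. Each cell gives these three in order.

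| p | f = 10% | f = 25% | f = 50% |
|---|---|---|---|
| 10% | 9.0%; 0.24; 0.21 | 7.5%; 0.60; 0.46 | 5.0%; 1.2; 0.71 |
| 20% | 18.0%; 0.48; 0.38 | 15.0%; 1.2; 0.71 | 10.0%; 2.4; 0.92 |
| 30% | 27.0%; 0.72; 0.52 | 22.5%; 1.8; 0.85 | 15.0%; 3.6; 0.98 |

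The spread, from 0.24 to 3.6 patients per arm, shows that the documents cannot settle the size.

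**The case against.** The best defence is that the two wordings serve different purposes. The protocol's wording says when to give the scale; it does not define a rate. Protocol 9.4.2 plans TEAE summaries by MedDRA term and leaves the detail to the SAP, so a preferred-term rule fits that plan and is more reproducible than site judgement. Because sites grade these events on the pruritus categories, many will probably be recorded as pruritus anyway. The Appendix 6 preference for a diagnosis applies only where one can be made. No test depends on this table, and the example intervals overlap almost entirely. Part of 8.5.6 is blacked out and the SAP sentence after the definition breaks off, so further handling may exist out of sight.

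Most of this stands and limits the point. It does not remove it: the definition sentence is complete, and it excludes a site-identified event coded elsewhere.

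Four stronger readings are tempting but unsupported:
- *The scores of missed cases would go unreported.* SAP 4.1 and 4.3 put eCRF data in listings. Only the pairing in the pruritus listing is at risk.
- *The protocol and SAP define conflicting pruritus rates.* The protocol defines no such rate; the gap is between what is collected and what is counted.
- *The string rule can only undercount site-identified cases.* It also counts coded events with no rating-scale record, so the two sets can differ in either direction. It can only fall short of their union.
- *The capital letter in 'Prur' drops further terms.* The SAP does not call for a case-sensitive match, and which dictionary terms would be affected is not in the documents.

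**Conclusion.** The point holds as a gap between collection and counting within SAP 9.2.3. A site-identified itch event coded to a term without 'Prur' is left out of every row of the pruritus summary, and out of the paired listing if that uses the same definition. It remains in the general TEAE tables and the eCRF listings.

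The size of the loss is unknown. Each patient affected is worth 4.2 points in an arm and 1.4 points in the pooled TERN-101 group, assuming the planned 24 per arm are all in the Safety Analysis Set and the patient has no other matching event. The table of p and f values is illustrative only. No hypothesis test, type I error rate or power is affected. This is an inexpensive improvement worth making to the description of the primary safety objective; it does not invalidate the safety analysis.

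**What to change.** Amend SAP 9.2.3, with the rule fixed before unblinding, to show two patient-level counts side by side:

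1. Patients with a TEAE whose preferred term contains 'prur', matched without regard to case.
2. Patients who meet item 1, or have site-completed pruritus eCRF details, or have a post-baseline rating-scale record.

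Base the pruritus listing on the second set, so that patients scored are reconciled with patients counted. Define the wider count by patient rather than by event: the scale is given per visit, and nothing visible in the documents ties a score to a particular AE.

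The cost is a few lines of SAP text and a small programming change on data already collected. The wider count is less specific and relies more on site judgement; keeping the preferred-term count beside it lets the reader see how much that matters. No clinical procedure changes.

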9.3. Clinical Safety Laboratory Evaluations

All laboratory assessments are specified in Appendix 1 of the study protocol. Laboratory parameters will be summarized in conventional units. Coagulation parameters, hemoglobin A1c, direct bilirubin, and indirect bilirubin will not be summarized.

Quantitative serum chemistry and hematology results will be summarized by treatment group using descriptive statistics at baseline and at each post-baseline visit. The change and percent change from baseline will also be summarized.

All clinical safety laboratory data will be presented in by-patient data listings. A separate listing for central laboratory normal ranges, by lab category, lab test, lab parameter, sex, and age, will be presented. Any local laboratory normal ranges for COVID-19 will be presented separately.

9.3.1. Treatment Emergent Abnormalities

Quantitative laboratory tests will be assigned grades based on National Cancer Institute Common Terminology Criteria for Adverse Events (NCI CTCAE) Version 5. For each applicable laboratory test, a treatment emergent abnormality will be defined as a post-baseline through Week 16 CTCAE grade increase of ≥ 2 grades.

The number and percentage of patients overall and by laboratory test, with any treatment emergent laboratory abnormality, CTCAE increase of ≥ 2 grades, will be presented. Similarly, the number and percentage of patients overall and by laboratory test, with CTCAE increase of ≥ 1 grade will be presented.

Estimated glomerular filtration rate (eGFR) is calculated by the central lab using the Chronic Kidney Disease Epidemiology Collaboration (CKD-EPI) equation. eGFR does not have a normal range within the central lab data. A normal range will be defined as ≥ 90 mL/min/1.73m².

LDL-c cannot be graded via NCI CTCAE version 5. For the purposes of treatment emergent abnormalities, LDL will be graded as follows:

- Optimal: < 100 mg/dL
- Near or Above Optimal: 100 – 129 mg/dL
- Borderline High: 130 – 159 mg/dL
- High: 160 – 189 mg/dL
- Very High: >189 mg/dL

LDL-c treatment emergent abnormalities will be summarized separately.

Listings will be presented for any patient with any treatment emergent laboratory abnormality (any increase in CTCAE grade). Normal ranges provided by the central laboratory will be presented in a listing.

9.3.2. Special Assessments of Potential Hepatotoxicity

Number and percentage of patients meeting each of the below criteria in [Table 9](#) will be summarized by treatment group.

Modified Hy's rule by Bjornsson ([Bjornsson 2005](#)), the incidence of patients with ALT or AST values >3 x ULN and total bilirubin >2 x ULN (based on the same blood draw of ALT, AST, and total bilirubin while on study drug, or within 30 days of last received dose) will be used to assess the potential for study drug-induced liver toxicity. The incidence rates of this laboratory abnormality constellation will be presented. Any patient meeting any of the criteria specified in [Table 9](#) will be presented.

Table 9: Modified Hy's Rule Laboratory Abnormalities

| Hepatocellular Injury and Liver Function Tests | Range of Test Values |
|---|---|
| AST | 3 to $4.99 \times \text{ULN}$ |
| | 5 to $9.99 \times \text{ULN}$ |
| | 10 to $19.99 \times \text{ULN}$ |
| | $\geq 20 \times \text{ULN}$ |
| ALT | 3 to $4.99 \times \text{ULN}$ |
| | 5 to $9.99 \times \text{ULN}$ |
| | 10 to $19.99 \times \text{ULN}$ |
| | $\geq 20 \times \text{ULN}$ |
| AST or ALT | 3 to $4.99 \times \text{ULN}$ |
| | 5 to $9.99 \times \text{ULN}$ |
| | 10 to $19.99 \times \text{ULN}$ |
| | $\geq 20 \times \text{ULN}$ |
| Total bilirubin | $> \text{ULN}$ |
| | $> 1.5 \times \text{ULN}$ |
| | $> 2 \times \text{ULN}$ |
| AST or ALT plus total bilirubin | $> 3 \times \text{ULN}$ (AST or ALT) plus $> 1.5 \times \text{ULN}$ (total bilirubin) |
| AST or ALT plus total bilirubin | $> 3 \times \text{ULN}$ (AST or ALT) plus $> 2 \times \text{ULN}$ (total bilirubin) |
| Alkaline phosphatase | $> 1.5 \times \text{ULN}$ |

ALT = alanine aminotransferase; AST = aspartate aminotransferase; ULN = upper limit of normal

LFT values in units of ULN will be calculated as the result/upper limit of normal.

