Of the 96 patients randomized, 24 patients will take part in an intensive PK and pharmacodynamic (PD) collection after the first dose and after the last dose of study drug. This includes 6 patients at each TERN-101 dose level, and 6 patients in the placebo group. Patients who are not participating in the PK/PD sub-study will have trough PK/PD sampling only.

The total duration of study participation will be approximately 24 weeks, consisting of an 8-week Screening Period, a 12-week Treatment Period and a 4-week Follow-up Period.

Disclosure Statement:

This is a parallel-group treatment study.

Number of Patients:

Approximately 96 patients will be randomly assigned to treatment with TERN-101 tablet or matching placebo.

Patients who are randomized but do not receive study drug for any reason may be replaced.

Study Centers Planned:

Approximately 40 centers in the United States.

Intervention Groups and Duration:

The total study duration will be approximately 24 weeks, consisting of an 8-week Screening Period, a 12-week Treatment Period and a 4-week Follow-up Period.

Screening Period

The 8-week Screening Period initiates upon signing an Informed Consent, at which point eligibility criteria will be reviewed. Each eligible patient will be scheduled for Week 0/Day 1.

Treatment Period

The 12-week double-blind, randomized Treatment Period will initiate at Week 0/Day 1 after confirming eligibility. The blinded study drug (TERN-101 tablet or placebo) will be orally administered once daily in the morning, without regard to food.

Patients will return to the site at Weeks 2, 4, 6, 8, and 12 for safety and laboratory assessments. Study drug will be dispensed at Week 0/Day 1, Week 4, and Week 8. Week 12 is the last day of treatment.

Intensive PK/PD sampling will be performed in 24 patients participating in the PK/PD sub-study after the first dose (Week 0/Day 1) and after the last dose of study drug (Week 12).

[figure not shown]
Imaging (MRI-PDFF) will be completed at Week 0, Week 6, and Week 12. An MRI is performed at early termination (ET) only if not done within the prior 4 weeks, and the patient has had at least 4 weeks of dosing.

Follow-up Period

All patients will return to site for follow up safety assessments at Week 16.

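### The combined Hy's-rule count in SAP 9.3.2 omits a patient whose enzyme and bilirubin limits are exceeded only on different blood draws

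*SAP*

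**What the plan says.** SAP 9.3.2 defines the modified Hy's-rule measure as "the incidence of patients with ALT or AST values >3 x ULN and total bilirubin >2 x ULN". The two results must be "based on the same blood draw of ALT, AST, and total bilirubin while on study drug", "or within 30 days of last received dose". The SAP says this incidence "will be used to assess the potential for study drug-induced liver toxicity".

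The same section also plans wider output. It summarises by arm the "Number and percentage of patients meeting each of the below criteria in" Table 9. The rows include ALT and AST bands from 3 x ULN upwards, total bilirubin alone (above ULN, 1.5 x ULN and 2 x ULN), and two combined rows (bilirubin above 1.5 x ULN and above 2 x ULN). "Any patient meeting any of the criteria specified in" Table 9 is to be presented. SAP 9.3 adds: "All clinical safety laboratory data will be presented in by-patient data listings".

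On timing of samples, the protocol synopsis says: "Patients will return to the site at Weeks 2, 4, 6, 8, and 12 for safety and laboratory assessments". A follow-up visit comes at Week 16.

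**The concern.** Bilirubin can rise after the enzymes have peaked. If ALT and AST have both fallen to 3 x ULN or below by the draw that shows bilirubin above 2 x ULN, no single sample meets both limits. The combined count is then zero for that patient, although both abnormalities occurred on treatment.

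Safety is the primary objective, and this constellation is the one the SAP names for judging possible liver toxicity. With about 24 patients per arm, one case decides whether the report says that no patient met the combined criterion.

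**Working it through.** The documents state no Hy's-rule rate, so there is no figure of theirs to reproduce. The check applies the definition.

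**1. Draw spacing** (Protocol 1.3, Schedule of Activities). Chemistry is scheduled on Days 1, 15, 29, 43, 57, 85 and 113.
- To Week 8: 14 days between draws.
- After Week 8: 85 − 57 = 28 and 113 − 85 = 28 days.
- With ±3-day windows, Week 8 to Week 12 can be (85 + 3) − (57 − 3) = 34 days.

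**2. Same-draw rule against a sequential rule.** Illustrative values in multiples of ULN, not trial data; AST is taken to be no higher than ALT.

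| Sequence | Enzyme draw (ALT / bilirubin) | Next draw (ALT / bilirubin) | Same-draw | Same or later draw |
|---|---|---|---|---|
| A | 8 / 1.2 | 2.5 / 2.5 | 0 | 1 |
| B | 8 / 1.2 | 4 / 2.5 | 1 | 1 |
| C | 8 / 2.5 | 2 / 1 | 1 | 1 |

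Only A is missed. The condition for a miss is that ALT and AST are both at or below 3 x ULN at every draw with bilirubin above 2 x ULN.

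**3. Can this happen without extra monitoring draws?** The Schedule of Activities refers to increased monitoring when ALT or AST is above 2 x baseline or above 5 x ULN. Take baseline ALT 2.5 x ULN, which entry allows because only values above 5 x ULN are excluded (Protocol 5.2). The triggers are then 2 × 2.5 = 5 x ULN and 5 x ULN.
- Day 57: ALT 4.5, bilirubin 1.2. Neither trigger is met.
- Day 85: ALT 2.8, bilirubin 2.4.
- Same-draw count 0; sequential count 1.

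**4. Speed of ALT decline.** The documents give none, so half-times h of 2, 7 and 14 days are assumed. Time to fall from M to 3 x ULN is h × log2(M/3).
- From 8: 2.8, 9.9 and 19.8 days.
- From 20: 5.5, 19.2 and 38.3 days.

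In step 3 ALT settles towards 2.5 rather than zero. The excess falls from 4.5 − 2.5 = 2.0 to 2.8 − 2.5 = 0.3, which takes log2(2.0/0.3) = 2.74 half-times. To fit in 28 days, h must be at most 28/2.74 = 10.2 days. A miss is possible, not certain.

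**5. Size of one case.**
- 1/24 = 4.2% of an arm; 1/72 = 1.4% of active patients.
- For scale, a zero count has a one-sided 95% upper bound of 1 − 0.05^(1/n): 11.7% for n = 24 and 4.1% for n = 72.

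**The case against.** The strongest reply is that the patient stays visible. The case appears in an enzyme row and in the bilirubin above 2 x ULN row, in the presentation of anyone meeting a Table 9 criterion, and in the listings. In arms of 24, a reader can match the two. This stands against any claim that the case disappears from the safety output. It does not supply a by-arm combined count, and the separate rows are a weak substitute: the 3 to 4.99 x ULN band can hold patients already at that level at entry, and patients with Gilbert syndrome may enrol (Protocol 5.2).

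Other points that stand:
- A reader might infer that every injury with a late bilirubin rise is left out. Sequence B shows otherwise: it is counted if ALT or AST is still above 3 x ULN.
- A reader might illustrate the gap with ALT at 6 x ULN and no draw for 28 days. That value passes the visible monitoring trigger, and Protocol 8.1.7 calls for clinically significant Grade 3 or 4 results to be repeated within 48–72 hours. Those draws can satisfy the same-draw rule, and Appendix 3, which is redacted, may add more.
- A reader might extend the same-draw condition to the bilirubin above 1.5 x ULN row. The text attaches it only to the 2 x ULN constellation.
- A reader might conclude that the measure errs only towards under-counting. Same-draw cases are indeed a subset of the sequential ones. But the limits are multiples of ULN, not of baseline, so a chronically raised enzyme can meet its half without drug injury.
- The primary laboratory endpoint (SAP 2.3.1 and 9.3.1) carries no same-draw condition.
- The contents list places 9.3.2 on page 42 and 9.3.3 on page 45, and Table 10 is not visible. Withheld text may hold a peak-value or non-concurrent display.

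**Conclusion.** The point holds in a narrow form. The combined incidence leaves out a patient who exceeds the two limits only on different draws, and the visible SAP offers no combined count that would include that patient. The documents do not support saying that delayed bilirubin rises are generally missed, or that such a patient is lost from the hepatotoxicity output.

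Each affected patient changes the count by 4.2 percentage points in a 24-patient arm, or 1.4 points across 72 active patients. The expected number is not given and is probably small. The conclusion rests on ALT falling fast enough between draws, on no intervening draw catching both limits together, and on no withheld text already covering the case. The change is worth making because it concerns the primary safety objective and needs no new data.

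**What to change.** Keep the same-draw row as it is. In SAP 9.3.2:
- Add a supplementary row to Table 9: AST or ALT above 3 x ULN with total bilirubin above 2 x ULN in the same draw or any later draw, on study drug or within 30 days of the last dose.
- List each such patient with both dates, baseline ALT and AST, and Gilbert status.
- State the timing rule for the combined row with bilirubin above 1.5 x ULN.

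A fixed 30-day pairing interval would not do: Week 8 and Week 12 draws can be 34 days apart within their windows, so it could miss the case it is meant to catch. If Table 10 or other withheld text already gives such a display, a cross-reference is enough.

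The cost is one or two sentences and one table row from data already collected. SAP Section 1 lets planned analyses change without an updated SAP if significant changes are reported in the CSR, but the rule is best fixed before unblinding. The small downside is that some unrelated bilirubin rises, and some patients with enzymes raised since entry, will be counted and must be reviewed from the listing.
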